1.4 Impulsive Aggression Diary (IA Diary)

Sponsor has developed and validated a new measurement tool to assess behaviors associated with IA. The impulsive aggression diary (IA diary) is an electronic observer-reported outcome (eObsRO) instrument that comprises an episodic diary (to be reported as soon as possible after the parent or other guardian or observer witnesses the child's IA behavior) and an evening diary (to enable at a minimum, completion of the diary once each day). The IA diary monitors the frequency of occurrence of 15 IA behaviors: Yelling, Screaming, Threatening, Scratching, Throwing, Slamming, Hitting Self, Arguing, Cursing, Name Calling, Shoving, Hair Pulling, Fighting, Hitting Others, Kicking Others. The development process followed FDA's "Guidance for Industry Patient-Reported Outcome Measures: Use in Medical Product Development to Support Labeling Claims." Through this process, the IA diary was demonstrated to be a psychometrically valid and reliable tool to assess IA in children (Sponsor Study 810P501).

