4.2 Schedule of Visits and Procedures

All subjects who are randomized and take any SM will be followed according to the protocol regardless of the number of doses of SM taken, unless consent for follow-up is withdrawn. The Sponsor, or the Sponsor's designee, must be notified of all deviations from the protocol visits or procedures, and these procedures, if applicable, will be rescheduled or performed at the nearest possible time to the original schedule. Subjects will be instructed to call study personnel to report any abnormalities during the intervals in between study visits and to come to the study site if medical evaluation is needed and as the urgency of the situation indicates. Unscheduled visits may be conducted at the discretion of the investigator throughout all study periods. The medical monitor must be contacted promptly in the event that any clinically significant findings or information are obtained during the unscheduled visit. This should be captured in the appropriate eCRF. For emergency and other unscheduled visits to a medical facility other than the study site, medical records will be obtained by the Investigator or qualified designee as source data for study follow-up.

[Table 1](#) presents the schedule of visits and procedures for the study.

Table 1: Schedule of Visits and Procedures

Phase	Pre-treatment		Treatment				Conversion/ Taper
	Screening	Baseline	Titration		Maintenance		
Period	1	2	3	4	5	6	7
VISIT NUMBER	1	2	3	4	5	6	7
DAY	-45	-15	1	8	15	36	43
WINDOW (DAYS)	≤45d prior to Visit 3	≥15d prior to Visit 3	0 ^c	7d±2d from Visit 3	14d±2d from Visit 3	21d±3d from Visit 5	7d±1d from Visit 6
Informed Consent/Assent ^a	X ^b						
R-MOAS, K-SADS-PL 2013 & Vitiello Aggression Scale	X						
Medical History	X		X ^d				
Demographics	X						
Physical Examination	X					X	
ECG (12-lead)	X			X		X	
Inclusion/Exclusion Criteria	X						
Randomization			X ^{b,e}				
Urine Drug Screen	X		X				
Urine Pregnancy Test ^f	X		X				X
Diary Training & Distribution or Evaluation		X	X ^e	X	X	X	
Vital Signs ^g	X						X
Weight, height, BMI	X		X	X	X	X	X
Hematology/chemistry/Urinalysis	X		X			X	X
PK Blood Sampling				X ^h	X ^h		
Columbia Suicide Severity Rating Scale (CSSRS)	X		X	X	X	X	X
Investigator CGI-S	X		X	X	X	X	
Caregiver and investigator CGI-I				X	X	X	
Efficacy scales (SNAP-IV, CHQ-PF28, PSI-4-SF)			X			X	
Safety Scales (Simpson-Angus, Barnes, AIMS)			X	X	X	X	X
Infrequent Behaviors Checklist			X	X	X	X	
Adverse Events			X	X	X	X	X

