Visit 2 will occur at least 15 days prior to Visit 3. Please note that, per protocol and within the EDC, Visit 1 and Visit 2 may occur on the same day.

1. Provide training for IA diary and dosing diary module
2. Distribute device
3. Assess and record concomitant medications

4.2.3 Visit 3

Visit 3 will occur at least 15 days following Visit 2 according to the Schedule of Visits and Procedures.

1. Administer efficacy scales (SNAP-IV, CHQ-PF28, PSI-4-SF)
2. Assess IA diary compliance / review training as necessary
3. Confirm eligibility to randomize to study medication treatment
4. Randomize subject via IWRS
5. Administer Investigator CGI-S
6. Administer Infrequent Behaviors Checklist

7. Administer safety scales (Simpson-Angus, Barnes Akathisia, AIMS)
8. Record height, weight, and BMI
9. Collect blood samples for hematology/chemistry
10. Collect urine samples for urinalysis, urine drug screen (all subjects), and pregnancy test (FOCBP only)
11. Administer C-SSRS
12. Record concomitant medication
13. Assess for any clinically significant change in Medical History
14. Dispense SM via IWRS.
15. Review training on dosing diary module
16. Assess adverse events (post-dose)

4.2.4 Visit 4

Visit 4 will occur 7 (± 2) days following Visit 3 according to the Schedule of Visits and Procedures.

1. Administer Investigator CGI-S
2. Administer caregiver and investigator-completed CGI-I
3. Administer Infrequent Behaviors Checklist
4. Administer safety scales (Simpson-Angus, Barnes Akathisia, AIMS)
5. Record height, weight, and BMI
6. Perform 12-lead ECG
7. Collect blood samples for PK analysis
8. Administer C-SSRS
9. Record concomitant medication
10. Review IA diary compliance and provide training as required
11. Collect AEs
12. Review dosing diary compliance and provide training as required

4.2.5 Visit 5

Visit 5 will occur 14 (± 2) days following Visit 3 according to the Schedule of Visits and Procedures.

1. Administer Investigator CGI-S
2. Administer caregiver and investigator-completed CGI-I
3. Administer Infrequent Behaviors Checklist
4. Administer safety scales (Simpson-Angus, Barnes Akathisia, AIMS)
5. Record height, weight, and BMI
6. Collect blood samples for PK analysis
7. Administer C-SSRS
8. Record concomitant medication
9. Review IA diary compliance and provide training as required
10. Collect AEs
11. Collect returned SM; assess treatment compliance
12. Review dosing diary compliance and provide training as required

13. Dispense SM

4.2.6 Visit 6

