4.3 Treatments

4.3.1 Treatments Administered

Subjects will take molindone hydrochloride extended-release tablet (SPN-810) or placebo twice each day (BID) with or without food, in the morning and in the evening, in addition to the stable dose of the optimized ADHD medication determined from the lead-in period. If initiating treatment before noon, patients should start with the morning dose; if after noon, the evening dose.

Subjects will be randomized to one of three treatments at Visit 3. Subjects will be titrated up to the final randomized total daily dose (TDD).

- Reference treatment
 - Treatment 1: Placebo tablets, PO, BID
- Test treatments
 - Treatment 2: Molindone extended-release tablets, 18 mg TDD, PO, BID
 - Treatment 3: Molindone extended-release tablets, 36 mg TDD, PO, BID

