6.3 Analysis Populations

The population of “all enrolled subjects” consists of all those screened subjects who meet the requirements for study participation and are entered in the Baseline period of the study. The population of “all randomized subjects” consists of all those enrolled subjects who complete the Baseline Period, meet the inclusion/exclusion criteria and are randomized.

Safety Population: will include all randomized subjects who received at least 1 dose of study drug.

Intent-to-Treat (ITT) Population: will include all subjects who received at least 1 dose of study drug and have a baseline and at least 1 valid post-randomization assessment of frequency of IA behaviors based on IA diary entry.

Per-Protocol (PP) Population: will include all of the subjects in the ITT population who completed the treatment period with 80% diary completion compliance and who did not have major protocol deviations.

PK population: will include all subjects in the safety population who had at least one PK sample drawn which had a quantifiable concentration for at least one analyte of interest.

The safety, ITT, PP, and PK populations are based on randomized treatment received.

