7 STATISTICAL ANALYSIS

7.1 *Analysis Populations*

The population of “all enrolled subjects” consists of all those screened subjects who meet the requirements for study participation and are entered in the Baseline period (i.e., distributed IA diary) of the study. The population of “all randomized subjects” consists of all those enrolled subjects who complete the Baseline Period, meet the inclusion/exclusion criteria and are randomized.

7.1.1 *Safety Population*

The safety population will include all randomized subjects who received at least 1 dose of study drug and have at least one post-randomization safety measurements.

7.1.2 *Intent-to-treat (ITT) Population*

The intent-to-treat population will include all subjects who received at least 1 dose of study drug and have a baseline and at least 1 valid post-randomization assessment of frequency of IA behaviors based on IA diary entry. Subjects will be analyzed according to the treatment to which they were randomized.

7.1.3 *Per Protocol (PP) Population*

The per protocol population will include all of the subjects in the ITT population who completed the treatment period (Completed Maintenance Visit 6) with 70% diary completion compliance and who did not have major protocol deviations. Diary compliance is calculated as

$$\text{diary compliance} = \frac{\text{number of days diary completed within the treatment period}}{\text{Number of treatment days}} \times 100\%$$

Detailed specification of the PP population will be provided prior to the database lock for the final analysis.

7.2 *Disposition of Subjects*

Subject disposition and reasons for screening failure will be summarized for screen-failed subjects (Table 14.1.1).

Subject randomization schedule will be listed. Subjects whose randomization codes are unblinded during the conduct of the study will be listed along with the reason for un-blinding (Listing 16.1.7).

The following summaries and listings will be based on all randomized subjects.

Subjects (n and %) who completed and discontinued from the study will be tabulated by the treatment group for (1) Randomized, (2) ITT, (3) Safety, and (4) PP populations (Table 14.1.2a – Table 14.1.2d). The primary reasons for study discontinuation will be included in the tabulation. The primary reasons may include any of the following:

- Subject withdrew consent
- Lost to follow-up
- Administrative reason
- Adverse event
- Investigator decision
- Failure to follow required study procedures
- Other

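### SAP 7.1.1 narrows the protocol's safety population to treated subjects with an undefined post-randomization safety measurement, without declaring the change

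*SAP*

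**What the plan says.** Protocol 6.3, with the same definition in the synopsis, reads: "Safety Population: will include all randomized subjects who received at least 1 dose of study drug". Dosing is the only condition beyond randomization. Protocol 6.5 also uses treated subjects as a synonym for this population.

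SAP 7.1.1 keeps randomization and dosing and then adds "and have at least one post-randomization safety measurements". SAP section 1 says the SAP supersedes the protocol's statistical methods, so the narrower set governs. SAP 3.6, the section for changes to the protocol's planned analyses, says only that the SAP will be updated if the protocol changes. It does not mention the safety population.

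ITT, in SAP 7.1.2 and protocol 6.3 alike, needs a dose and that the subject "have a baseline and at least 1 valid post-randomization assessment of frequency of IA behaviors based on IA diary entry". It needs no safety measurement.

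**The concern.** Whether a treated child counts in the safety analyses now depends on something that happens after randomization. Children who stop early are the least likely to supply it, and some may stop because they tolerate the drug poorly. SAP 7.8 bases all safety summaries on this population.

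The populations also stop nesting. Under the protocol, every randomized ITT subject is in Safety, because ITT requires a dose. Under the SAP, a child can contribute to the primary efficacy analysis and yet be missing from the AE denominators.

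Protocol 4.2 and SAP 3.2 commit to following everyone who takes any study medication, however few doses. Protocol 6.1 asks for an amendment when principal features change. No reason for the narrower set is given in either document.

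**Working it through.** The plan states no figure on this point, so there is nothing to reproduce. The check compares the definitions, follows one subject through them, and then illustrates the size.

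**Can a subject be in ITT but not in Safety?**

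- *Diary.* The instrument includes "an evening diary (to enable at a minimum, completion of the diary once each day" (protocol 1.4). The caregiver completes it at home. SAP 5.1 starts the treatment period at Day 2, so a Day 2 entry can meet the ITT condition without a clinic visit.
- *Next clinic visit.* Visit 4 falls "7d±2d from Visit 3" (protocol Table 1), that is, 7 − 2 = 5 to 7 + 2 = 9 days after randomization.
- *Safety check on the day of randomization.* Protocol 4.2.3 lists "Assess adverse events (post-dose") at Visit 3. But protocol 4.3.1 says: "If initiating treatment before noon, patients should start with the morning dose; if after noon, the evening dose". A first dose in the evening can fall after the clinic procedures.
- *Loss.* "Lost to follow-up" is a listed discontinuation reason in SAP 7.2.

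A child who doses on the evening of Day 1, has a Day 2 diary entry and is never heard from again therefore meets ITT. Whether that child meets Safety depends on what counts as a safety measurement, which the SAP does not say.

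**Which outputs use the affected denominator?** (SAP Appendix 2 and sections 7.2 to 7.8)

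- *Affected:* the AE incidence tables (14.3.1.x), prior and concomitant medications (14.1.12.1 and 14.1.12.2), medical history (14.1.8), the Safety versions of disposition (14.1.2c, 14.1.3c) and demographics (14.1.7b), and the listing of all AEs (16.2.3.1.1).
- *Not affected:* exposure and compliance (14.1.11, on ITT), disposition on the randomized population (14.1.2a, 14.1.3a, Listing 16.2.1.1), and the listings of SAEs, deaths, AE discontinuations and AEs of special interest (16.2.3.1.2 to 16.2.3.1.5, on the randomized population).
- *Little or no effect:* by-visit percentages for other safety measures. SAP 6.1 already leaves subjects with missing values out of percentage denominators.

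**Illustration of size.** The documents give no rate of loss before a first safety observation, so 1% to 2% of treated subjects is an assumption. Arm sizes are 330/3 = 110 (protocol 6.10) and 153 (SAP 3.5), taking all randomized subjects as treated. The AE frequency of about 20% is also assumed.

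Subjects excluded per arm (k):

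- N = 110: 1.1 to 2.2, so 1 to 2.
- N = 153: 1.5 to 3.1, so 2 to 3.

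With x subjects having the event, the rate is x/N under the protocol and x/(N − k) under the SAP, if the excluded subjects have no recorded event. The ratio of the two rates is N/(N − k).

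- N = 110, x = 22: 22/110 = 20.0% becomes 22/109 = 20.2% (k = 1) or 22/108 = 20.4% (k = 2). Ratios are 1.009 and 1.019.
- N = 153, x = 31: 31/153 = 20.3% becomes 31/151 = 20.5% (k = 2) or 31/150 = 20.7% (k = 3). Ratios are 1.013 and 1.020.

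The relative rise is about 1% to 2%. With k = 0 nothing changes.

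**The case against.** The best defence is that the condition may exclude nobody. The SAP says post-randomization, not post-dose, and SAP 5.4 counts AEs among the safety variables. Protocol 4.3.6 has subjects start dosing during Visit 3, where an AE check is scheduled. Protocol 4.2.3 also lists the movement scales, blood samples and C-SSRS after the randomization step and before dispensing. If that order is chronological, even pre-dose measurements would satisfy the wording. Early discontinuers are due the Visit 7 safety procedures as well. This stands as a limit on size, but it does not justify the phrase. If the phrase excludes nobody, it serves no purpose. If it excludes somebody, it departs from the protocol.

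It also stands that the plan partly covers the gap. Table 14.1.6 counts each population and Listing 16.2.1.3 gives each subject's reason for exclusion. The AE incidence tables would still use the narrower set.

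A reader might infer more than the documents support:

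- *Everyone who takes drug and is then lost leaves Safety.* Only those lost before any safety observation could leave.
- *Harm would be hidden.* If excluded subjects had events that were dropped, rates would fall, for example from 22/110 = 20.0% to 21/109 = 19.3%. But a recorded AE would ordinarily be a safety observation and keep the subject in.
- *Exposure, or every safety denominator, is distorted.* The output list under the working shows otherwise.
- *The SAP's summary of changes should have recorded this.* That log covers changes since SAP version 1.0, so its silence is not an omission. The place for a departure from the protocol is SAP 3.6.

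**Conclusion.** The definitions conflict, the narrower one governs, and the change is undeclared and rests on an undefined term. That follows from the text and needs no assumption. The practical effect is small and may be zero. Under the assumed 1% to 2% early loss it is about 1 to 3 subjects per arm and a relative rise of 1% to 2% in AE rates, which would be unlikely to alter a safety conclusion. The point is worth making because the correction is nearly free and restores both the treated-subject denominator and the nesting of ITT within Safety.

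**What to change.** In SAP 7.1.1, delete "and have at least one post-randomization safety measurements" so that the definition matches protocol 6.3. Report by arm the number of treated subjects with no post-dose safety assessment, for example as a line in Table 14.1.6.

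If the sponsor prefers to keep the restriction, SAP 7.1.1 should define the qualifying measurement, including whether the Visit 3 post-dose AE check counts, and SAP 3.6 should declare and justify the departure.

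The cost is one phrase in the SAP and one table line before database lock. It needs no new data and leaves the sample size and the efficacy analyses unchanged.

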7.5 Baseline Disease Characteristics

Summaries of baseline disease characteristics will be based on the ITT population, with the exception of medical history which will be presented for the Safety population.

Subject incidence (n and %) of medical history will be tabulated by MedDRA System Organ Class (SOC) and Preferred Term (PT) for each treatment group as per Section [7.8.1](#) (Table 14.1.8).

R-MOAS and Vitiello Aggression Scale will be summarized by treatment group as per Section [6.1](#) (Tables 14.1.9 - 14.1.10).

All baseline disease characteristics will be listed (Listing 16.2.1.5 – Listing 16.2.1.7).

7.6 Treatments

7.6.1 Treatment Compliance and Extent of Exposure

Summaries of treatment compliance and exposure will be based on the ITT population.

Duration of exposure is defined as the total number of days a subject is exposed to any study treatment. This will be calculated for each subject by taking the difference between the date of last dose minus the date of the first dose, plus 1 (date of last dose – date of first dose +1).

Duration of Treatment exposure will be summarized using descriptive statistics (n, mean, SD, median, minimum, and maximum).

Percent of SM compliance is defined as

Treatment Compliance

$$= \frac{\text{Number of Tablets Dispensed} - \text{Number of Tablets Returned}}{4 \times (\text{Date of Last Dose} - \text{Date of First Dose} + 1)} \cdot 100\%.$$

Each subject is expected to take 4 tablets per day as in the following. Subjects randomized to placebo group will take 2 placebo tablets in the morning and 2 placebo tablets in the evening. Subjects randomized to SPN-810 █ mg will take one █ mg active tablet and 1 placebo tablet in the morning and one █ mg active tablet and 1 placebo tablet in the evening. Subjects randomized to SPN-810 █ mg will take two █ mg active tablets in the morning and two █ mg active tablets in the evening. For each treatment, SM compliance will be summarized with number of subjects (n and %) by compliance category (<80%, 80-120%, and >120%). SM compliance will also be summarized as a continuous variable using descriptive statistics (n, mean, standard deviation, median, minimum, and maximum) for each treatment.

Summaries of treatment compliance and exposure will be presented separately for the Titration Period, Maintenance Period, and combined Titration and Maintenance Periods (Table 14.1.11 and Listing 16.2.1.8).

7.6.2 *Prior and Concomitant Medications*

Prior and concomitant medications will be tabulated separately based on the Safety Population. The number (n and %) of subjects taking at least one medication and the number (%) of subjects taking each medication at the WHODD preferred term level will be tabulated by treatment group, Anatomical-Therapeutic-Chemical classification 3 (ATC3), and PT. Subjects taking the same PT medication twice will only be counted once (Table 14.1.12.1 and Table 14.1.12.2).

A subject data listing will be provided to include the reported medication name, the WHODD PT, ATC4, study day and pertinent subject information (Listing 16.2.1.9.1 and Listing 16.2.1.9.2).

A separate data listing will include subjects who received prohibited medications (Listing 16.2.1.9.3).

7.7 *Efficacy Analyses*

7.7.1 *Primary Efficacy Analysis*

The primary analysis is based on the ITT population and the primary efficacy endpoint is the percent change (PCH_T) in the frequency (unweighted score) of IA behaviors per 7 days in the treatment period relative to the Baseline period calculated over the number of days with non-missing IA diary data.

The primary efficacy analysis will be performed using the Wilcoxon rank-sum test to compare the medians of each of the two doses of SPN-810 (█ mg and █ mg) with the median of the Placebo. The Hodges-Lehmann estimate of the difference (SPN-810 dose minus placebo) and the associated 95% confidence interval (CI) around the difference will be calculated. To protect the overall Type-I error rate from inflation due to sample size re-estimation and multi-dose to placebo comparisons, p-values will be adjusted using the method described in Section 6.8. The statistical analysis will be presented in the table along with the summary of the change from baseline frequency for Stage 1 and Stage 2 data (Table 14.2.1.1). The daily IA behavior diary will be listed. The daily frequency, the derived 7-day frequency for each week, and the derived 7-day frequency for the treatment period will be included (Listing 16.2.2.1.1 – Listing 16.2.2.1.2).

Box plots of Wilcoxon scores will be created for █ mg dose SPN-810 and Placebo, and 36 mg dose SPN-810 and Placebo, separately, using SAS PROC NPAR1WAY.

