7.8 Safety Analyses

Subject safety is assessed by AEs, labs, vital signs, 12-lead ECGs, and findings from the physical examinations. The occurrence of neurological side effects will be assessed by looking at any worsening in scores for each of the Simpson-Angus scale, Barnes Akathisia scale, and AIMS. Suicidal ideation and suicidal behavior will be measured by C-SSRS. All summaries related to safety analyses will use the safety population and will be presented by treatment groups.

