7.8.1 Adverse Events

AEs will be summarized using subject incidence table by treatment period (titration, maintenance, combined titration and maintenance, and tapering). An overview of TEAE will be presented. This table will include numbers and percentages of subjects experiencing at least 1 TEAE, study drug-related TEAE, AE leading to study drug discontinuation, severe TEAE, serious TEAE, related TESAE, AESI, and TEAE with outcome of death (Table 14.3.1.1).

Additionally, the number and percent (%) are calculated based on the number of unique subjects within each category (e.g., preferred term) by treatment group. A subject reporting multiple events of the same category will be counted only once for that category. For summary purpose, AE relationship to the study drug will be grouped into “Unrelated” for “unrelated” or “unlikely related” and “Related” for “possibly”, “probably”, or “definitely related”. For subjects with more than one event coded to the same PT, the subjects will be counted for the categories with the strongest relationship and the greatest severity. The following subject incidence tables will be presented.

- TEAEs by PT (Preferred Term) sorted by the decreasing order of subject incidence in the combined active dose group (Table 14.3.1.2.1 – Table 14.3.1.2.3)
- TEAEs by SOC (System Organ Class) and PT sorted alphabetically (Table 14.3.1.3.1 – Table 14.3.1.3.3)
- Study Drug-Related TEAEs by SOC and PT (Table 14.3.1.4.1 – Table 14.3.1.4.3)
- Severity of TEAEs by SOC and PT (Table 14.3.1.5.1 – Table 14.3.1.5.3)
- TESAEs by SOC and PT when applicable (Table 14.3.1.6)

- Number and percent of patients reporting common AEs ($\geq 5\%$ in any group) by PT (Table 14.3.1.7.1 – Table 14.3.1.7.3)
- TEAEs leading to study drug discontinuation by SOC and PT (Table 14.3.1.8)
- Treatment Emergent AESI by SOC and PT (Table 14.3.1.9)

Where warranted by the subject incidence, these same tables may be presented by treatment period (Titration, Maintenance and Conversion/Tapering).

A subject data listing will be provided for all adverse events (Listing 16.2.3.1.1). Included in the listing are the reported term, PT, SOC, TEAE flag, study day when AE starts, duration, relationship, severity, action taken, outcome, and seriousness category.

Data listings will be provided for subjects who die on study, experience SAEs, have TEAEs leading to study drug discontinuation, or AEs of special interest (Listing 16.2.3.1.2 – Listing 16.2.3.1.5).

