| 14.1.11 | Exposure to Study Medication and Compliance | ITT Population |
| 14.1.12.1 | Prior Medications by ATC Code and Preferred Term | Safety Population |
| 14.1.12.2 | Concomitant Medications by ATC Code and Preferred Term | Safety Population |
| 14.2.1.1 | Analyses of PCH in the Frequency of IA Behaviors During the Treatment Period - Primary Analysis | ITT Population |
| 14.2.1.2.1 | Analyses of PCH in the Frequency of IA Behaviors During the Treatment Period - Sensitivity Analysis, Multiple Imputation with MAR Assumption | ITT Population |
| 14.2.1.2.2 | Analyses of PCH in the Frequency of IA Behaviors During the Treatment Period - Sensitivity Analysis, Multiple Imputation with MNAR Assumption | ITT Population |
| 14.2.1.2.3 | Analyses of PCH in the Frequency of IA Behaviors During the Maintenance Period - Sensitivity Analysis | ITT Population |
| 14.2.1.2.4 | Analyses of PCH in the Frequency of IA Behaviors During the Treatment Period - Supplementary Analysis | PP Population |
| 14.2.1.3 | Descriptive Statistics for Frequency of IA Behaviors Per 7 Days and Change from Baseline by Study Period | ITT Population |
| 14.2.1.4 | Percent Change from Baseline to Treatment Period in Frequency of IA Behaviors: Adjustment for Covariates using Randomization-Based Approach of Dmitrienko and Koch | ITT Population |
| 14.2.1.5a | Analyses of PCH in the Frequency of IA Behaviors During the Treatment Period by Gender - Primary Analysis | ITT Population |
| 14.2.1.5b | Analyses of PCH in the Frequency of IA Behaviors During the Treatment Period by Age - Primary Analysis | ITT Population |

| | | |
|-----------|--|----------------|
| 14.2.1.5c | Analyses of PCH in the Frequency of IA Behaviors During the Treatment Period by Race - Primary Analysis | ITT Population |
| 14.2.2 | Investigator Clinical Global Impression – Improvement (CGI-I) Score by Visit | ITT Population |
| 14.2.3 | Caregiver Clinical Global Impression – Improvement (CGI-I) Score by Visit | ITT Population |
| 14.2.4 | Investigator Clinical Global Impression – Severity (CGI-S) Score and Change from Baseline by Visit | ITT Population |
| 14.2.5.1 | Child Health Questionnaire Parent Form 28 (CHQ-PF28) - Item Scores and Change from Baseline to Visit 6 | ITT Population |
| 14.2.5.2 | Child Health Questionnaire Parent Form 28 (CHQ-PF28)-Component Scores and Change from Baseline to Visit 6 | ITT Population |

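### Exposure and compliance are summarised only on the diary-dependent ITT set, so dosed children without a valid post-randomization diary can be in the adverse event tables but not in the exposure table

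*SAP*

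**What the plan says.** SAP 7.6.1 fixes the analysis set for this topic: "Summaries of treatment compliance and exposure will be based on the ITT population". The table list in SAP Appendix 2 agrees, giving Table 14.1.11 as "Exposure to Study Medication and Compliance | ITT Population". No Safety version of the table is listed, and Listing 16.2.1.8 (drug accountability and compliance) has a blank population field.

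The sets are defined as follows.

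- **ITT (SAP 7.1.2):** at least one dose, and subjects must "have a baseline and at least 1 valid post-randomization assessment of frequency of IA behaviors based on IA diary entry".
- **Safety (SAP 7.1.1):** randomized subjects who "received at least 1 dose of study drug and have at least one post-randomization safety measurements".
- **Safety (Protocol 6.3):** "will include all randomized subjects who received at least 1 dose of study drug", with no further condition.

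On safety reporting, SAP 7.8 says: "All summaries related to safety analyses will use the safety population and will be presented by treatment groups". SAP 7.8.1 adds that "AEs will be summarized using subject incidence table by treatment period". SAP 7.6.2 puts prior and concomitant medications on Safety, as SAP 7.5 does for medical history. SAP 7.4 shows demographics on ITT, Safety and PP. Protocol 6.7 defines duration of exposure but names no population, so the ITT choice comes from the SAP alone.

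**The concern.** Exposure tells the reader how many children took the drug and for how long, and it is read next to the adverse event tables. Here the two are reported for the same periods (titration, maintenance and both combined) but on different sets. The exposure set depends on an efficacy instrument, the caregiver diary, which has no bearing on whether a child took tablets.

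The gap can arise under the protocol's own procedures. Protocol 4.2.7 applies the Visit 7 procedures to children who stop early, and these include adverse events, EPS scales, vital signs and laboratory samples. A child who leaves within days can thus enter the Safety set. SAP 5.1 starts the treatment-period diary on Day 2 and assigns Day 1 to baseline, so a child dosed on Day 1 with no later diary has no treatment-period frequency. Such a child could appear among the adverse events leading to discontinuation and be missing from the exposure table. In a trial of an antipsychotic in children aged 6 to 12, a reader will want the exposure of every treated child.

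**Working it through.** The mismatch follows from the definitions alone. The documents give no figure to reproduce, because they do not say how many dosed children will lack a valid post-randomization diary or how long those children were on drug. The arithmetic below only illustrates the scale.

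**Inputs from the documents**
- Treatment phase: 2 + 3 weeks = 35 days (SAP 3.3.2).
- Dropout: about 20% (SAP 3.5, Protocol 6.10).
- Randomization targets: 330 (Protocol 6.10); 153 × 3 = 459 (SAP 3.5). These are targets, not numbers dosed.

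**Assumed inputs**
- f, the share of dosed children with no valid post-randomization diary: 1%, 2%, 5%.
- e, their mean days on drug: 1 to 7, with 35 as the counter-case in which dosing continued without diaries.
- E, the mean days in ITT: 35 if all complete. If 20% drop out after a mean of 17 days (assumed), E = 0.8 × 35 + 0.2 × 17 = 31.4.

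**Mean duration.** The mean over all dosed children is (1 − f)E + f·e. The ITT mean exceeds it by f(E − e) days:

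| f | e | E = 35 | E = 31.4 |
|---|---|---|---|
| 1% | 1 | 0.34 | 0.30 |
| 1% | 7 | 0.28 | 0.24 |
| 2% | 1 | 0.68 | 0.61 |
| 2% | 7 | 0.56 | 0.49 |
| 5% | 1 | 1.70 | 1.52 |
| 5% | 7 | 1.40 | 1.22 |
| 1% | 35 | 0 | −0.04 |
| 5% | 35 | 0 | −0.18 |

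For e of 1 to 7 days the excess is 0.24 to 1.70 days, or about 1% to 5% of the mean over all dosed children (0.24/31.16 = 0.8%; 1.70/33.30 = 5.1%). In the counter-case it is zero or slightly negative.

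**Number exposed.** ITT omits f × N children: 3.3 to 16.5 of 330, or 4.6 to 23 of 459, for f of 1% to 5%.

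**Total subject-days (n × mean).** The ITT shortfall is f·e / [(1 − f)E + f·e]. With E = 35:
- f = 1%, e = 1: 0.01/34.66 = 0.03%.
- f = 5%, e = 7: 0.35/33.60 = 1.0%.
- e = 35: 1.0% at f = 1% and 5.0% at f = 5%.

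**Compliance.** SAP 7.6.1 divides tablets dispensed minus returned by 4 × the child's own days from first to last dose. Leaving early shortens the denominator as well, so it does not in itself lower compliance. A child who leaves without returning tablets would score high. The effect of the exclusion on the compliance categories has no determined sign.

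**Adverse events.** The tables are subject incidences on Safety. Table 14.1.11 does not enter them, so no percentage changes.

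**The case against.** The strongest reply is that this is a label with little behind it. Randomization requires 80% baseline diary compliance, and one valid post-randomization diary is enough for ITT, so few dosed children should fall out. As a rough check, take 80% daily completion and independent days. A child on drug for three days then misses both Day 2 and Day 3 with probability 0.2 × 0.2 = 4%. Losing 5% of 459 (23 children) that way would need 23/0.04 = 575 three-day dropouts, more than will be randomized. The differing n would also be largely traceable through Table 14.1.6 (analysis populations), Listing 16.2.1.3 (reasons for exclusion) and the disposition tables.

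Part of this stands. The upper end of the assumed range is probably high, although missed diaries may cluster in children who are leaving. Traceability explains a difference in n, but it does not supply the missing exposure data in summary form.

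A reader might also infer stronger conclusions, which the documents do not support:
- *Exposure is overstated.* This can apply only to duration, and only if the excluded children had shorter exposure. The number exposed and total subject-days go the other way. The minimum need not move: a child dosed for one day with a Day 2 diary is still in ITT.
- *Compliance is biased upward.* The formula gives no such direction.
- *Adverse event rates have the wrong denominator.* They are incidences on Safety, and SAP 7.8.1 describes no exposure-adjusted rate.
- *The bias is largest in the arm with most early loss.* No arm-specific early loss is given.
- *The SAP contradicts the protocol on this set.* Protocol 6.7 names none.

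**Conclusion.** The point holds as a mismatch of analysis sets. It is minor, and it rests on the text without any assumption: exposure and compliance are tied to the diary, while adverse events and concomitant medications are not. Every dosed child without a valid post-randomization diary is missing from Table 14.1.11, so the number exposed and total subject-days are understated whenever such a child exists.

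That mean duration is somewhat too high is a probable inference, because children with no diary after dosing are most likely early leavers. Its size is unknown. The range of about 0.2 to 1.7 days depends wholly on the assumed 1% to 5% affected and 1 to 7 days on drug, and it vanishes or slightly reverses if dosing went on without diaries.

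Relabelling alone is not quite enough. The SAP Safety set adds a post-randomization safety measurement to the protocol's dose-only rule. Under the SAP wording neither set contains the other: a dosed child with a diary but no safety measurement would be in ITT and not in Safety.

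**What to change.** 1. In SAP 7.6.1 and Table 14.1.11, present exposure and compliance on the Safety population. Add compliance on ITT if it is wanted for reading the efficacy results.
2. State the population for Listing 16.2.1.8.
3. Reconcile the Safety definition in SAP 7.1.1 with Protocol 6.3 so that every dosed child is counted in exposure.

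The cost is a population label in one SAP section, one table title and one listing title, plus one sentence in the Safety definition. No new data are needed, and the primary analysis is untouched.
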